1.1.2 Secondary Objective(s)

Secondary objectives will include the evaluation of differences in overall surgical procedure time, operation room (OR) time, length of stay, procedure costs, quality of life measures including pain, and range of motion (ROM).

1.1.3 Other Objective(s)

The difference in the safety profiles for both wound closure procedures will be evaluated through the analysis of the incidence of wound complications including dehiscence, wound infections, and other adverse events.

1.2 STUDY ENDPOINTS

1.2.1 Primary Efficacy Endpoint(s)

The primary endpoint will be the total time required to close the surgical incisions between treatment groups. The time to close each surgical incision is defined as the time in minutes between placements of the first suture throws in the deep tissue to the completion of Intradermal layer closure (capturing the suturing time only).

1.2.2 Secondary Efficacy Endpoint(s)

Secondary efficacy endpoints include:

1. Duration of procedure (Total Operation Time): defined as the time in minutes elapsed from first incision to the skin closure;
2. Overall operating room (OR) time: defined as the time in minutes from the patient entering to exiting the OR;
3. Length of stay between surgery and discharge;

4. TKA related Quality of Life (QoL) assessments:

a. Knee Pain: pain at rest and pain during mobilization is measured using a 10 centimeter Visual Analogue Scale (VAS) in which patient is asked to describe degree of pain with 0 being no pain and 10 being the worst pain;

b. Health-related Quality of Life (EQ-5D-3L): patient is asked to confirm his/her health state by selecting the most appropriate level for each of the following 5 dimensions. Refer to Table 1.

- Mobility
- Self-care
- Usual activities
- Pain/discomfort
- Anxiety/depression

Table 1: EQ-5D-3L

By placing a tick in one box in each group below, please indicate which statements best describe your own health state today.

Mobility

I have no problems in walking about

I have moderate problems in wlaking about

I am unable to walk about

Self-care

I have no problems washing or dressing myself

I have moderate problems washing or dressing myself

I am unable to wash or dress myself

Usual Acitivities (i.e work, study, housework, family or leisure activities)

I have no problems doing my usual activities

I have moderate problems doing my usual activities

I am unable to do my usual activities

Pain/Discomfort:

I have no pain or discomfort

I have moderate pain or discomfort

I have extreme pain or discomfort

Anxiety/Depression

I am not anxious or depressed

[figure not shown]
I am moderate anxious or depressed

I am extremely anxious or depressed

To help people say how good or bad a health state is, we have drawn a scale (rather like a thermometer) on which the best state you can imagine is marked **100** and the worst state you can imagine is marked **0**.

We would like you to indicate on this scale how good or bad your own health is today, in your opinion. Please do this by drawing a line from the box below to whichever point on the scale indicates how good or bad your health state is today.

Your own
health state
today

1.2.3 Safety Endpoints

Safety endpoints include:

1. The incidence of SSI following surgery as defined by:

a. CDC criteria^[1]:

1) Superficial incisional SSI:

Infection occurs within 30 days after the operation and infection involves only skin or subcutaneous tissue of the incision and at least one of the following:

- Purulent drainage, with or without laboratory confirmation, from the superficial incision;
- Organisms isolated from an aseptically obtained culture of fluid or tissue from the superficial incision;
- At least one of the following signs or symptoms of infection: pain or tenderness, localized swelling, redness, or heat and superficial incision, is deliberately opened by surgeon, unless incision is culture-negative;
- Diagnosis of superficial incisional SSI by the surgeon or attending physician.

Do not report the following conditions as SSI:

- Stitch abscess (minimal inflammation and discharge confined to the points of suture penetration);
- Infection of an episiotomy or new born circumcision site;
- Infected burn wound;
- Incisional SSI that extends into the fascial and muscle layers (see deep incisional SSI).

Note: Specific criteria are used for identifying infected episiotomy and circumcision sites and burn wounds.

2) Deep incisional SSI:

Infection occurs within 30 days after the operation if no implant is left in place or within 1 year if implant is in place and the infection appears to, be related to the operation and infection involves deep soft tissues (e.g., fascial and muscle layers) of the incision and at least one of the following:

- Purulent drainage from the deep incision but not from the organ/space component of the surgical site;
- A deep incision spontaneously dehisces or is deliberately opened by a surgeon when the patient has at least one of the following signs or symptoms: fever ($>38^{\circ}\text{C}$), localized pain, or tenderness, unless site is culture-negative;
- An abscess or other evidence of infection involving the deep incision is found on direct examination, during reoperation, or by histopathologic or radiologic examination;
- Diagnosis of a deep incisional SSI by a surgeon or attending physician. Notes:
- Report infection that involves both superficial and deep incision sites as deep incisional SSI;
- Report an organ/space SSI that drains through the incision as a deep incisional SSI.

3) Organ/Space SSI:

Infection occurs within 30 days after the operation if no implant is left in place or within 1 year if implant is in place and the infection appears to, be related to the operation and infection involves any part of the anatomy (e.g., organs or spaces), other than the incision, which was opened or manipulated during an operation and at least one of the following:

- Purulent drainage from a drain that is placed through a stab wound into the organ/space;
- Organisms isolated from an aseptically obtained culture of fluid or tissue in the organ/space;
- An abscess or other evidence of infection involving the organ/space that is found on direct examination, during reoperation, or by histopathologic or radiologic examination;
- Diagnosis of an organ/space SSI by a surgeon or attending physician.

No confirmatory culture will be required unless deemed by the physician per local standard of care to provide appropriate treatment to subject.

b. ASEPSIS Score (only for patients with confirmed SSI): assesses severity of wound infection using numerical scoring (as opposed to the CDC's absence or

presence of SSI and type). The ASEPSIS Wound Score evaluates would characteristics and additional treatments as predictors of infection that may develop once the subject leaves the hospital. These include the presence of serous exudates, erythema, purulent exudates, separation of deep tissues, antibiotics, drainage of pus, wound debridement, isolation of bacteria, and requirement for inpatient stay. Surgeons assess each parameter and provide a numerical score based upon objective criteria of wound appearance and clinical consequences of the infection. Extra points were added for antibiotic treatment of SSI (10 points), drainage of pus under local anesthesia (5 points), debridement of the wound under general anesthesia (10 points), isolation of bacteria from the wound (10 points), and an inpatient stay of more than 14 days (5 points). An overall score, ranging from 0 to 100, is then calculated to define wound severity according to the proportion of the wound affected by each of these characteristics ^[2, 3]. Refer to Table 2;

2. Use Acute Inflammatory Response Evaluation (AIRE) score measuring inflammatory tissue reaction. Of note, an AE will be reported when the score is >1 . Refer to Table 3;
3. Incidence of wound separation or dehiscence requiring intervention;
4. Incidence of delayed wound healing events;
5. Incidence of wound closure related adverse events and serious adverse events;

Table 2: ASEPSIS Score

Wound Characteristic	Proportion of Wound Affected					
	0	<20	20-39	40-59	60-79	>80
Serous Exudate	0	1	2	3	4	5
Erythema	0	1	2	3	4	5
Purulent Exudate	0	2	4	6	8	10
Separation of Deep Issue	0	2	4	6	8	10
Points are scored for daily wound inspection.						
Additional Treatment		Points				
Antibiotics		10				
Drainage of Pus under local anesthesia		5				
Debridement of Wound (General Anesthesia)		10				
Serous Discharge*		Daily 0-5				
Erythema*		Daily 0-5				
Purulent Exudate*		Daily 0-10				
Separation of Deep Tissues*		Daily 0-10				

Isolation of Bacteria	10
Stay as In-patient Prolonged Over 14 Days	5

*Given scores on 5 of 7 days and the highest weekly score used.

Category of Infection	
Total Score**	Definition
0-10	Satisfactory Healing
11-20	Disturbance of Healing
20-30	Minor Wound Infection
31-40	Moderate Wound Infection
>40	Severe Wound Infection

**Total Score calculated adding scores for individual wound characteristics and additional treatment.

Table 3: Acute Inflammatory Response Evaluation (AIRE) Score

Score	Erythema	Oedema	Pain	Temperature
0	None observed	None observed	None	None
1	Slight blanching redness along incision closure line	Slight increase in tissue firmness (turgor)	Pain at site with pressure	Slightly warmer compared to adjacent skin
2	Moderate redness extending < 2 mm	Pitting of skin around incision with touch	Pain at site with touch	Definitely warmer compared to adjacent skin
3	Intense redness extending > 2 mm	Tense firmness of skin around incision	Continuous pain	Radiating heat at incision site

1.3 SUMMARY OF THE STUDY DESIGN

1.3.1 General Study Design and Plan

This is a multicenter, single blind, prospective, randomized controlled study in patients undergoing elective TKA and meeting the study's eligibility criteria. Eligible patients will be randomized on 1:1 basis to have the surgical incision closed with either [REDACTED] or conventional sutures. Wound closure and surgical procedure times will be determined perioperatively. Patients will remain blinded to the type of sutures utilized for closure of the incision.

The schedule of events is depicted in Table 4 below.

Table 4: Schedule of Events

Event	Visit 1	Visit 2	Visit 3	Visit 4	Visit 5
	Baseline/ Screening ^a	Randomization	Procedure	Post-Op through Discharge ^b	30-42 days ^c (post procedure)
Informed consent	X				
IWRS/IVRS ^d		X			
Inclusion/Exclusion	X	X			
Urine/blood pregnancy test	X				
Demographics	X				
Medical/Surgical history	X		X		
Physical examination ^e	X			X	X

	Visit 1	Visit 2	Visit 3	Visit 4	Visit 5
Event	Baseline/ Screening ^a	Randomization	Procedure	Post-Op through Discharge ^b	30-42 days ^c (post procedure)
Knee pain VAS	X			X	X
EQ-5D-3L	X			X	X
Concomitant medications ^f	X	X	X	X	X
Length of stay ^g				X	
Health Economic				X	
Procedural data ^h			X		
Adverse events			X	X	X
Wound			X	X	X
SSI/ASEPSIS score ⁱ				X	X
AIRE score				X	X
Study completion					X

- a. To be performed within 30 days of surgery.
- b. Data will be collect on 3-5 days after surgery (expect for the length of stay and health economic data).
- c. Unless withdrawn from the study, subject's status will be confirmed at the time of in-person visit at 30-42 days following surgery. If possible, an in-person visit will be scheduled to confirm status for patients withdrawn prematurely from the study for any reason.
- d. Interactive web response system/ Interactive voice response system.
- e. The physical examination at baseline/screening visit includes height, weight and ROM of knee, and the post-procedure physical examination only includes ROM of knee.
- f. Including pain medications and antibiotics (except for anesthesia medications).
- g. Defined as time between procedure and discharge.
- h. Procedure time, overall OR time, intra-operative device failure rates, operating room resource utilization (if applicable), and anesthesia method (e.g., general or lumbar anesthesia).
- i. ASEPSIS score will be applied only after SSI confirmed.

1.3.2 Randomization and Blinding

Randomization will occur if the patient meets all inclusion criteria and does not meet any exclusion criteria. Each case will be randomized to one of two groups (STRATAFIX or conventional sutures) in a 1:1 ratio. The only difference between the groups will be the suturing material and technique.

Blinding practices for this study will include the following:

Patients: Patients will be informed of the 1:1 randomization between the different suturing material and technique, but will remain blinded as to which implant they actually received until after they have completed all study follow-up.

Implanting surgeon: It is not possible to blind the implanting physician due to the different suturing technique and products.

Medical Records: All medical records (source documents) documenting the implant procedure through hospital discharge and all follow-ups will not be blinded because the devices used will be described in the operation record.

Monitors: Monitors will not be blinded because the detachable labels provided with the product identify the product and may be used in the study device accountability records and patient research file for the purpose of device accountability and source document validation.

1.3.3 Sample Size and Statistical Power Considerations

The proposed sample size of 92 patients per arm (184 total) is considered adequate to test the hypothesis that [REDACTED] can reduce the time for incision closure compared to conventional sutures. Based upon a review of the literature, the mean incision closure time was assumed to be 16.89 minutes for conventional sutures, being calculated as a weighted (based on number of subjects) mean of the means observed in the studies reviewed. The studies reported incision closure times ranging between 14.4 to 26.5 minutes [4-8]. It is expected that the [REDACTED] can reduce the incision closure time by [REDACTED] compared to conventional sutures; therefore, the assumed mean closure time for [REDACTED] is [REDACTED] minutes. The standard deviations observed in the reviewed literature range from [REDACTED] to [REDACTED] minutes for the conventional sutures; the standard deviation for this study was conservatively assumed to be [REDACTED] minutes in both groups for several reasons, such as the lack of data for [REDACTED] and that this patient sample may be older and with larger Body Mass Index (BMI). The distribution of incision closure time is assumed to be normal.

The statistical hypotheses for the primary endpoint are as follows:

- H_0 : Mean Barbed \geq Mean conventional suture tested against the alternative hypothesis
- H_a : Mean Barbed $<$ Mean conventional suture;

Where:

- The assumed mean time to incision closure in conventional group is [REDACTED] minutes;
- The mean time to closure in [REDACTED] is [REDACTED] minutes;

- The assumed standard deviations in the two groups are both [REDACTED]

Based upon these assumptions, a total seventy-seven (77) evaluable subjects per arm will achieve 90% power to detect a difference of [REDACTED] minutes (expected mean for [REDACTED] of [REDACTED] minutes and the conventional group of [REDACTED] minutes) with estimated group standard deviations of [REDACTED] using a one-sided two-sample t-test. The assumed one-sided significance level is [REDACTED]

If the higher limit of the one-sided 97.5% confidence interval for the difference in the Mean [REDACTED] time minus the Mean closure time for conventional suture is smaller than 0, then it will be concluded that [REDACTED] is considered to be superior to conventional suture. The sample size is adjusted to 92 per arm to account for a 16% withdraw rate [9-12].

2 STATISTICAL CONSIDERATIONS

2.1 GENERAL CONSIDERATIONS

All descriptive statistics for continuous variables will be reported using number of subjects (missing), mean, standard deviation (SD), median, quartile (Q1, Q3), minimum and maximum. Categorical variables will be summarized as number of subjects (missing), and frequencies along with the associated percentages.

2.2 DEFINITIONS OF ANALYSIS SETS

There will be three analysis sets defined:

- Modified Intent-to-treat set (mITT set) consists of all randomized subjects who had the surgical incisions closed using the randomized suture
- Evaluable [or Per-Protocol (PP)] set consists of all mITT subjects who have no major protocol violations.
- Safety set consists of all subjects who receive surgery.

Major protocol deviations are deviations that have an impact on the primary endpoint, or that have an impact on the randomization assignment. These will be determined prior to database lock.

2.3 DEFINITIONS AND CONVENTIONS FOR DATA HANDLING

2.3.1 Baseline Definition

Baseline: The baseline value is defined as the most recent value reported just prior to Procedure. Visit 1 (Baseline/Screening) occurs prior to the study procedure (performed within 30 days of surgery), and the evaluation performed at this Visit will be considered the “baseline” evaluation for analysis.

2.3.2 Study Day

Study Day will be calculated from the reference start date and will be used to show the day of assessment or start/stop day of events.

Reference start date (Day 0) is defined as the day of randomization.

Event Day = (date of event – reference start date).

2.3.3 Follow-Up Time

The follow-up duration for a subject is the time from randomization to the last non-missing visit post-baseline.

2.3.4 Analysis Visit Windows

No analysis window period will be used. Endpoint data will be collected at visit 3 (Surgical Procedure), visit 4 (Post-Op through Discharge), and visit 5 (30-42 Days Post Procedure).

2.3.5 Missing Data Handling Rules

All summaries of efficacy endpoints will be performed only on subjects who are randomized, and only observed data will be summarized. There will be no imputation for missing data or imputation of data for early terminated subjects.

2.4 MULTIPLE COMPARISONS/MULTIPLICITY

All secondary endpoints and/or any further sensitivity or exploratory analyses for the primary and secondary endpoints will serve as supportive evidence only and therefore no adjustment for multiple comparisons will be performed.

2.5 POOLING OF CENTERS

No adjustment for this multicenter study will be performed.

3 STATISTICAL ANALYSES

3.1 SUBJECT INFORMATION

3.1.1 Disposition of Subjects

The number of subjects screened and the frequencies (percentages) of subjects who failed screening and the reasons for screen failure will be summarized, based on data reported on the Visit1 - Baseline/Screening CRF. The distribution of the number of randomized subjects enrolled by each site will be summarized for each treatment group and overall.

Completion of Study Treatment: The frequencies (percentages) of randomized and treated subjects who completed study treatment and who terminated early from study will be

summarized according to the reason for subject's early termination, based on data reported on both the Visit 2- Randomization CRF and End of Study CRF.

3.1.2 Protocol Deviations

A deviation (any activity conducted outside the parameters established by the study protocol) can be identified from a number of sources. Potential sources include, but are not limited to: a member of the Investigator's staff, a Sponsor representative during monitoring visits, or a member of the data management or statistical groups when entering or analyzing data. Regardless of the source, it is crucial to document the deviation. The Principal Investigator (PI) will report protocol deviations to the IRB as required by the IRB procedures.

Major protocol deviations are deviations that have an impact on the primary endpoint, or that have an impact on the randomization assignment.

The protocol deviations will be identified prior to database lock .

The frequencies (percentages) of subjects in the mITT Population will be presented by treatment group according to deviation type, and a listing of all collected protocol deviations cases will be presented in an appendix listing.

3.1.3 Demographics and Baseline Characteristics

Demographic and baseline characteristics for all enrolled subjects, as well as for the mITT subjects, will be summarized for each treatment group and overall, using descriptive statistics. Continuous demographic and baseline characteristics including age at time of informed consent, height, weight, BMI, and ROM of Knee will be summarized descriptively by number of subjects (missing), mean, standard deviation, median, quartile (Q1, Q3), minimum, and maximum; categorical variables including gender, race, ethnicity, education, occupation categories, urine/blood pregnancy test results, knee pain, Health-Related Quality of Life (EQ-5D-3L) will be summarized descriptively by frequencies along with the associated percentages.

3.1.4 Medical History

The Medical/Surgical History will be coded by Medical Dictionary for Regulatory Activities (MedDRA 20.0 or higher Version) or higher version. The frequencies (percentages) of subjects reporting a medical/surgical history, as recorded on the CRF, will be summarized for all enrolled subjects, as well as for the mITT set, for each treatment group and overall. A subject data listing of medical and surgical history will be provided.

3.1.5 Concomitant Medication and Non-drug Treatment

All terms for Concomitant medications recorded on the CRF will be coded using the World Health Organization (WHO) Drug Dictionary (JUN 1st 2017).

The Non-drug Treatment will be coded by Medical Dictionary for Regulatory Activities (MedDRA 20.0 or higher Version) or higher version.

The frequencies (percentages) of subjects who took concomitant medications or non-drug treatment will be summarized for all enrolled subjects, as well as for the mITT set by treatment group and overall.

3.1.6 Treatment Compliance

Descriptive summary statistics will be provided for compliance for each treatment group and all patients in the mITT set. The frequencies and percentage of patients participating in visit 3 through visit 5 will be provided.

3.2 EFFICACY ANALYSES

3.2.1 Primary Efficacy Analysis

3.2.1.1 Primary Analysis

The primary efficacy endpoint will be analyzed using the mITT and Per-Protocol analysis sets. The mITT analysis will be considered primary analysis.

For the primary efficacy endpoint, a one-sided 97.5% confidence interval for the difference in treatment group means (Mean [REDACTED] closure time minus the Mean closure time for conventional suture) will be constructed using the t-distribution. If the higher limit of the confidence interval is smaller than 0, then it will be concluded that [REDACTED] is considered to be superior to conventional suture.

The primary efficacy endpoint will be summarized by treatment group, reporting number of subjects (missing), mean, standard deviation, median, quartile, minimum and maximum.

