#### **4.5.2 Determination of Sample Size**

The proposed sample size of 92 patients per arm (184 total) is considered adequate to test the hypothesis that [REDACTED] can reduce the time for incision closure compared to conventional sutures. Based upon a review of the literature, the mean incision closure time was assumed to be [REDACTED] minutes for conventional sutures, being calculated as a weighted (based on number of subjects) mean of the means observed in the studies reviewed. The studies reported incision closure times ranging between 14.4 to 26.5 minutes [5, 7-10]. It is expected that the [REDACTED] can reduce the incision closure time by [REDACTED] % compared to conventional sutures; therefore, the assumed mean closure time for [REDACTED] is [REDACTED] minutes. The standard deviations observed in the reviewed literature range from 3.43 to 8.5 minutes for the conventional sutures; the standard deviation for this study was conservatively assumed to be [REDACTED] minutes in both groups for several

reasons, such as the lack of data for [REDACTED] and that this patient sample may be older and with larger BMI. The distribution of incision closure time is assumed to be normal.

The statistical hypotheses for the primary endpoint are as follows:

- H0: Mean Barbed  $\geq$  Mean conventional suture tested against the alternative hypothesis
- Ha: Mean Barbed  $<$  Mean conventional suture;

Where:

- The assumed mean time to incision closure in conventional group is [REDACTED] minutes;
- The mean time to closure in [REDACTED] is [REDACTED] minutes;
- The assumed standard deviations in the two groups are both 8.

Based upon these assumptions, a total seventy seven (77) evaluable subjects per arm will achieve 90% power to detect a difference of [REDACTED] minutes (expected mean for [REDACTED] of [REDACTED] minutes and the conventional group of [REDACTED] minutes) with estimated group standard deviations of [REDACTED] using a one-sided two-sample t-test. The assumed one-sided significance level is 0.025.

If the higher limit of the one-sided 97.5% confidence interval for the difference in the Mean [REDACTED] time minus the Mean closure time for conventional suture is smaller than 0, then it will be concluded that [REDACTED] is considered to be superior to conventional suture. The sample size is adjusted to 92 per arm to account for a 16% withdraw rate [25-28].

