#### 4.5.4 Analysis of Primary and Secondary Efficacy Endpoints

For the primary efficacy endpoint, a one-sided 97.5% confidence interval for the difference in treatment group means (Mean [REDACTED] closure time *minus* the Mean closure time for conventional suture) will be constructed using the t-distribution. If the higher limit of the confidence interval is smaller than 0, then it will be concluded that [REDACTED] is considered to be superior to conventional suture.

The primary efficacy endpoint will be analyzed using the mITT and Per-Protocol analysis sets. The mITT analysis will be considered primary analysis. All secondary efficacy endpoints will be analyzed using the mITT analysis set.

All efficacy endpoints (see section 2.1) will be summarized descriptively by treatment group. The continuous variables will be summarized descriptively by number of subjects, mean, standard

deviation, minimum, and maximum. Categorical data will be summarized descriptively by frequencies along with the associated percentages. No inferential statistics will be generated for the secondary efficacy endpoints.

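### The primary closure-time comparison is valid but leaves out age and BMI, which are collected at baseline; prespecifying them could make it modestly more precise at almost no cost.

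*SAP*

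**What the plan says.** SAP 3.2.1.1 rests the primary conclusion on "a one-sided 97.5% confidence interval for the difference in treatment group means". Protocol 4.5.4 has the same analysis and says the interval "will be constructed using the t-distribution". Superiority is declared if the upper limit for barbed minus conventional lies below zero. The Protocol synopsis describes the same interval. No covariate is named in any of these places.

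The sizing in Protocol 4.5.2 matches this analysis. It is done "using a one-sided two-sample t-test", with SD 8 in both arms, and concludes that "a total seventy seven (77) evaluable subjects per arm will achieve 90% power to detect a difference of" a difference that is redacted. It also states: "The assumed one-sided significance level is 0.025".

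The same section explains why the SD was set conservatively. It gives several reasons, among them the lack of data for the device and that "this patient sample may be older and with larger BMI". SAP 1.3.3 repeats this.

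Protocol 3.4.1 collects year of birth, height and weight at Visit 1. SAP 3.1.3 lists "Continuous demographic and baseline characteristics including age at time of informed consent, height, weight, BMI, and ROM of Knee" for descriptive tables by arm, and neither age nor BMI is used in any comparison. Nothing else in the plan uses them:

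- Protocol 3.4 (Randomization) and SAP 1.3.2 give no stratification factor.
- SAP 2.4 refers to sensitivity analyses only in general terms.
- SAP 3.4 marks exploratory analysis as not applicable.

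**The concern.** A patient characteristic that predicts closure time adds to the residual variance of a raw comparison of means. If it is known before randomisation, putting it in the model removes that part of the variance and leaves the treatment contrast unchanged as a difference in means. Here the data are already collected and derived, and the sponsor thought age and BMI relevant enough to mention when choosing the SD.

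At stake is the precision of the single inferential comparison, since Protocol 4.5.4 and SAP 3.2.2 exclude inference on the secondary efficacy endpoints. Adjustment also removes the effect of whatever age or BMI imbalance happens to occur. That is credible only if the model is fixed in advance, because an adjusted result added after an imbalance has been seen would carry little weight. The question concerns patient covariates and is separate from the decision not to adjust for centre (Protocol 4.6.2, SAP 2.5).

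**Working it through.** **Inputs from the documents.** SD 8 in both arms, one-sided α 0.025, 90% power, 77 evaluable and 92 randomised per arm, 16% withdrawal (Protocol 4.5.2); control mean 16.89 min (SAP 1.3.3).

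**Inputs assumed.** The target difference is redacted. A 25% reduction is inferred: 0.25 × 16.89 = 4.2225 min. The R² of age plus BMI for closure time is not given, so 0 to 15% is taken as a range.

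**Step 1: reproduce the plan.** With difference 4.2225, SD 8 and the noncentral t distribution, n = 77 per arm and power at 77 is 90.2%. Solving backwards, 77 per arm at exactly 90% power implies a difference of 4.206 min, or 24.9% of 16.89, which supports the 25% inference. Reductions of 20% or 30% would need 119 or 54 per arm. The inflation also reproduces: 77 / 0.84 = 91.67, rounded up to 92.

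**Step 2: unadjusted precision.** The distance from estimate to limit is t(0.975; 2n − 2) × 8 × √(2/n).

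- n = 77: 1.976 × 8 × 0.1612 = 2.55 min
- n = 92: 1.973 × 8 × 0.1474 = 2.33 min

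**Step 3: adjusted precision, net of cost.** With two covariates and N = 2n, the effective SD is 8 × √[(1 − R²) × (1 + 2/(N − 5))], with N − 4 degrees of freedom. The second factor is the average price of estimating two coefficients: 1 + 2/149 = 1.0134 at 77 per arm and 1 + 2/179 = 1.0112 at 92 per arm.

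| Analysis | Effective SD, n = 77 | Power, n = 77 | Effective SD, n = 92 | Distance to limit, n = 92 |
|---|---|---|---|---|
| Unadjusted | 8.00 | 90.2% | 8.00 | 2.33 min |
| Adjusted, R² = 0 | 8.05 | 89.8% | 8.04 | 2.34 min |
| Adjusted, R² = 5% | 7.85 | 91.3% | 7.84 | 2.28 min |
| Adjusted, R² = 10% | 7.64 | 92.6% | 7.63 | 2.22 min |
| Adjusted, R² = 15% | 7.42 | 93.9% | 7.42 | 2.16 min |

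**Step 4: break-even.** Adjustment pays once (1 − R²) × (1 + 2/(N − 5)) falls below 1. That is R² above 1 − 1/1.0112 = 1.1% at 92 per arm, and above 1 − 1/1.0134 = 1.3% at 77 per arm. If R² is zero, the limit at 92 per arm moves out by about 0.6% (2.340 / 2.327 = 1.006).

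**Step 5: chance imbalance.** At 92 per arm, a 1.96-standard-error imbalance in the combined age and BMI predictor shifts the raw difference by 1.96 × 8 × √R² × √(2/92). This is 0.52 min at R² = 5% and 0.73 min at R² = 10%. The unadjusted interval already allows for such shifts on average; adjustment removes the particular one that occurs.

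**The case against.** The strongest reply is that nothing here is wrong. The t interval is valid under randomisation and matches the test used for sizing. The sample size was set for 90% power without covariates, so the stated power is not overstated on this ground. All of that stands.

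A reader might infer that the plan itself identifies age and BMI as sources of closure-time variability and then ignores them. The documents do not support that. The sentence in the sample-size sections is hedged, is one of several reasons, and compares this sample with those in the literature. It reports no association with closure time within a trial population. A larger SD in an older, heavier sample could also reflect wider scatter about the mean, which a linear covariate term does not remove. Adjustment helps only if age and BMI predict the mean closure time among the patients enrolled.

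A reader might also take the imbalance figures in step 5 as bias. They are not, because randomisation puts that variation into the unadjusted standard error.

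The gain may also be small. Eligibility limits the spread (age under 80, BMI not above 40; Protocol 3.2), and incision length is recommended to stay within 15 cm (Protocol 3.3.1). At R² = 5% the limit tightens by about 0.05 min, roughly 3 seconds, against an inferred difference of 4.22 min. The source of variability that the protocol addresses by design is the surgeon, through the suggestion of at most two closing surgeons per site.

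These points limit the size and priority of the suggestion. They do not remove it, because the data are in hand and the downside is bounded.

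**Conclusion.** The point holds as a low-cost efficiency improvement. The plan's analysis is valid and its power claim is sound. What it forgoes is a modest gain: about 1 to 4 percentage points of power at 77 per arm for R² of 5 to 15%, and 0.05 to 0.17 min off the distance to the limit at 92 per arm. Below an R² of about 1% there is no gain, and at zero there is a loss of about 0.4 points of power.

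The textual facts are firm: the analysis is unadjusted, both covariates are collected at baseline, and no adjusted analysis is specified. The size is not firm. It rests on an assumed R² range and an inferred 4.22-min difference. Only the SD of 8, the error rate, the control mean and the sample sizes come from the documents.

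**What to change.** Before database lock, state in SAP 3.2.1.1 and Protocol 4.5.4 that the barbed-minus-conventional difference is estimated from a linear model of closure time on arm, age (continuous) and BMI (continuous). Keep the one-sided 97.5% upper limit and the below-zero rule, and report the unadjusted t interval as supportive.

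The same analysis or decision rule also appears in the Protocol synopsis, Protocol 4.5.2 and SAP 1.3.3. These should be aligned so that the documents do not describe two different primary analyses. The 77 and 92 per arm can stay, described as a conservative calculation without covariates.

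The cost is wording in five places and one model in the analysis program. It takes two degrees of freedom, and the limit is about 0.6% wider if the covariates turn out not to be prognostic. No new data, visits or patients are needed.
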